## 11. STATISTICAL CONSIDERATIONS

### 11.1. Sample Size

A total of 32 participants will be enrolled to this study. The primary objective is to evaluate the 16-week progression free survival rate. The CONKO-003 study reported a median OS with best supportive care in this subject population to be 2.3 months. Therefore, the null hypothesis assumes a median PFS of 6 weeks. This corresponds to a 16-week PFS rate of approximately 0.15. A single-stage design will be used to test the hypothesis that the 16-week PFS rate is less than or equal to 0.15. If at least 8 of the 32 subjects are alive and progression free at 16 weeks, the null hypothesis will be rejected (based on an exact binomial test) and regorafenib therapy may be considered for further evaluation in this subject population. Assuming a one-sided alpha = 0.10 significance level, this sample size will provide at least 90% power to reject the null hypothesis, assuming the true 16-week progression free survival rate is 0.35. An increase in the 16-week PFS rate of 0.20 in the context of this Phase II study is considered clinically relevant.

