Attempts to improve upon the rather modest benefit of single-agent gemcitabine have met with mixed success. Phase III studies have combined gemcitabine with 5-FU, cisplatin, irinotecan, pemetrexed, capecitabine, oxaliplatin, exatecan, cetuximab, and bevacizumab without a survival benefit over gemcitabine alone. A randomized phase III study demonstrated a clinically small but statistically significant survival benefit with the addition of the epidermal growth-factor receptor (EGFR) tyrosine kinase inhibitor erlotinib to standard gemcitabine therapy (median OS=6.37 months vs. 5.91 months, HR=0.82, 95% CI: 0.69-0.99). More recently, the addition of nab-paclitaxel to gemcitabine demonstrated an improvement in survival compared to gemcitabine alone (median OS 8.5 months vs. 6.7 months, HR=0.72, 95% CI: 0.617-0.835, p=0.000015), which establishes this combination as an appropriate first-line standard treatment option in patients with advanced pancreatic cancer.

The only non-gemcitabine based regimen to improve outcomes is the multi-agent combination of FOLFIRINOX (oxaliplatin, irinotecan, leucovorin, and infusional fluorouracil). A 342 patient randomized study demonstrated a clinically and statistically significant improvement in OS (overall survival) for FOLFIRINOX compared to single-agent gemcitabine (11.1 months vs. 6.8 months, HR 0.57, 95% CI: 0.45-0.73, p<0.0001), which makes it an appropriate front-line choice for healthier patients who can tolerate this relatively toxic regimen.

Unfortunately, the prognosis for patients who have had failure of previous gemcitabine-based therapy is dismal with a median expected survival of less than 2.5 months. The randomized phase III CONKO-003 study tested second-line salvage therapy with oxaliplatin, folinic acid, and 5-fluorouracil compared to best-supportive care, but was stopped early after only 46 patients had been accrued. Although this study suggested the possibility of clinical benefit with oxaliplatin-fluoropyrimidine based therapy, the very small sample size precludes any definitive conclusions. Currently, no standard second-line treatment options exist for advanced pancreatic cancer. Thus, we wish to examine regorafenib in this setting.

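### Does the 6-week null median for PFS undermine the 10% type I error of the 8-of-32 rule?

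*Combined protocol and SAP*

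**What the plan says.** Section 11.1 cites a median overall survival of 2.3 months on best supportive care, from the randomised second-line trial described in section 2.1. It then sets the null median and converts it to a landmark: "Therefore, the null hypothesis assumes a median PFS of 6 weeks. This corresponds to a 16-week PFS rate of approximately 0.15". It names no survival distribution for the conversion.

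The formal test is then set on the rate, not on the median: "A single-stage design will be used to test the hypothesis that the 16-week PFS rate is less than or equal to 0.15". The rule is to reject if 8 or more of 32 subjects are alive and progression free at 16 weeks, by an exact binomial test. On the error rates the section says: "Assuming a one-sided alpha = 0.10 significance level, this sample size will provide at least 90% power", where the alternative is a 16-week rate of 0.35.

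Section 11.4.4.1 (Primary Analysis) and the Protocol Summary repeat 15% as the null, with one-sided alpha 0.10.

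**The concern.** Section 11.1 reads as a chain: a clinical premise (a 6-week median), a derived rate (0.15), then a test of that rate. A reader may take the 10% limit on false positives to apply if regorafenib leaves median PFS at 6 weeks. The usual constant-hazard conversion gives 0.1575, which rounds to 0.16, so the protocol's figure is slightly low, in the direction that makes rejection easier.

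The difference seems to matter because the rule is tight. Its size passes 0.10 once the null rate exceeds 0.1514. If the 6-week exponential median were the null, 8 of 32 would be too lenient, and 9 of 32 would lose the stated power. On that reading the rounding is what makes the cut-off admissible.

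The premise also looks thin. The only figure cited for it is an OS median from a trial stopped after 46 patients, about which section 2.1 says "the very small sample size precludes any definitive conclusions". An error of a week in the median is plausible, and the rejection probability climbs quickly with the null rate.

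**Working it through.** **Inputs.** From section 11.1: n = 32; reject at 8 or more; null rate 0.15; alternative rate 0.35; one-sided alpha 0.10; power at least 0.90; null median PFS 6 weeks. The exponential and Weibull curves below are assumptions, because the protocol names no model.

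**Step 1: the plan's own design.** With X the number of subjects alive and progression free at 16 weeks, X ~ Binomial(32, p).

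- Size: P(X ≥ 8 | p = 0.15) = 0.0958, which is below 0.10.
- Power: P(X ≥ 8 | p = 0.35) = 0.9182, which is above 0.90.

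The design reproduces. A search over n from 20 to 59 finds 32 the smallest sample size that meets both targets.

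**Step 2: median to landmark, exponential.** S(16) = 2^(-16/m), with m the median in weeks.

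- m = 6: 2^(-2.667) = 0.1575.
- In reverse, S(16) = 0.15 requires m = 16 × ln 2 / (-ln 0.15) = 11.09 / 1.897 = 5.85 weeks.
- A median reported as 6 to the nearest week covers 5.5 to 6.5 weeks, that is, rates from 2^(-16/5.5) = 0.133 to 2^(-16/6.5) = 0.182. The value 0.15 lies inside that range.

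**Step 3: the 8-of-32 rule at other null rates.**

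| Null rate | Exponential median (weeks) | P(X ≥ 8) | P(X ≥ 9) |
|---|---|---|---|
| 0.15 | 5.85 | 0.096 | 0.041 |
| 0.1514 | 5.87 | 0.100 | not computed |
| 0.1575 | 6 | 0.119 | 0.054 |
| 0.2051 | 7 | 0.328 | 0.194 |

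With 9 of 32, power at 0.35 is 0.842.

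**Step 4: shape.** Hold the median at 6 weeks and let the curve be Weibull with shape k: S(16) = 0.5^((16/6)^k).

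| Shape k | S(16) | P(X ≥ 8) |
|---|---|---|
| 0.9 | 0.187 | 0.239 |
| 1.0 (exponential) | 0.157 | 0.119 |
| 1.03 | 0.149 | 0.093 |
| 1.1 | 0.130 | 0.049 |

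A hazard that rises very slightly (k about 1.03) reproduces the protocol's 0.15 from exactly 6 weeks. A falling hazard moves the rate the other way.

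**Step 5: what a formal null of 0.1575 would require.** Keeping alpha at or below 0.10 and power at or above 0.90 at 0.35, the smallest exact design is n = 35 with rejection at 9 or more (size 0.088, power 0.911). This is a redesign, not a correction to section 11.1.

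**The case for a change.** The strongest argument for acting is that the word approximately is only harmless when the rule can absorb the approximation, and this rule can absorb very little. The room above 0.15 is 0.1514 - 0.15 = 0.0014, whereas the exponential conversion is off by 0.1575 - 0.15 = 0.0075. At an exponential 6-week median no cut-off with 32 subjects meets both targets: 8 fails on size and 9 fails on power. The protocol offers no reason to expect a rising hazard, so it cannot claim the shape that rescues the figure. A sentence naming the model and giving the rejection probability at 0.157 would cost nothing.

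The arithmetic in that argument stands, and so does the lack of slack. It does not show that a stated figure is wrong. The 10% belongs to the exact test of 15%, and there it holds. Little slack is normal when the smallest admissible sample size is chosen for a discrete test.

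The point about the thin historical basis is weaker than it looks. The caution in section 2.1 concerns whether the oxaliplatin regimen gives benefit, not the best-supportive-care median used in section 11.1. Uncertainty about the historical rate is common to single-arm designs with a fixed null, and a more exact conversion of a rounded median would not remove it.

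Restating the null as 0.157 while keeping 8 of 32 would do harm. It would put a size of 0.119 beside the alpha of 0.10 in section 11.4.4.1, creating a contradiction that the protocol does not now contain.

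**Conclusion.** No change is needed. The test is of a 16-week rate of 15%, and for that test the stated sample size, cut-off, alpha (exact 0.096) and power (exact 0.918) are all correct. The link from a 6-week median to 0.15 is a rounding in the rationale: on an exponential curve the matching median is 5.85 weeks, a difference of 0.15 weeks, or about one day.

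The 0.119 is a correct answer to a different question, namely how often the rule rejects if PFS is exponential with a median of exactly 6 weeks. It rests on a model that the documents do not name. Over Weibull shapes from 1.1 to 0.9 the same median gives 0.049 to 0.239, so the median alone does not fix the size.

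Naming the conversion model or writing 5.85 weeks would be a tidier rationale, but it would alter no sample size, cut-off, analysis or conclusion. When the result is read, 8 successes in 32 should be understood as just clearing a 15% benchmark, with little margin if the true historical rate is somewhat higher.

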### 11.2. Endpoint Definitions

#### 11.2.1. 16-Week Progression Free Survival

Progression free survival will be calculated from a recorded binary variable determined for each subject indicating whether or not the patient experienced disease progression or death from any cause during the 16 week period following the start of treatment. Disease progression can be objectively determined as per Section 10.2 or progression can be subjective as determined by the Investigator. Evidence for subjective progressions must be documented in the medical records. The binary variable described above will be calculated for the primary objective.

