### **3.6. Replacement**

Subjects who withdraw consent after receiving first dose of study drug will not be replaced. Screen failures may be replaced.

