#### **4.3.8. Radiology and Tumor Measurements**

A CT (computed tomography) scan with oral and intravenous contrast of the chest, abdomen and pelvis will be performed within 28 days prior to the first dose of regorafenib (screening scan). After enrollment, scans will then be performed every eight weeks (+/- 2 weeks). A contrast-enhanced MRI of the abdomen and pelvis and an uncontrasted CT scan of the chest may be substituted if clinically necessary; however, subsequent studies must be performed using the same imaging modality throughout the study period. Scans will be submitted for Central Radiology review per Section 10.1.4.

Every effort will be made to obtain imaging studies and tumor assessments every 8 weeks (+/- 2 weeks) until documented progression for subjects who had a complete response, partial response, or stable disease, and/or discontinued study therapy due to toxicity or reasons other than progressive disease.

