#### 11.2.2. Progression Free Survival

PFS is defined as the duration of time from enrollment to the study to time of

progression or death. Disease progression can be objectively determined as per Section 10.2 or progression can be subjective as determined by the investigator. Evidence for subjective progressions must be documented in the medical records. For surviving subjects who do not have documented disease progression, PFS will be censored at the date of last radiologic assessment. For subjects who receive subsequent anti-cancer therapy prior to documented disease progression, PFS will be censored at the date of last radiologic assessment prior to the commencement of subsequent therapy. Subjects who experience a PFS event immediately following an interval equal to two or more scheduled CT assessments will be censored at the date of the last assessment prior to the first missed assessment.

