## **11.4. Analysis Methods**

### **11.4.1. Timing of Analysis**

While not planned as a formal multistage analysis, we will be evaluating safety and efficacy in data reviews throughout the course of the study. The analysis for the primary objective will occur after all 32 patients have either progressive disease, died, or have at least 16 weeks of follow up time after the treatment start date. Preliminary analysis of the secondary endpoints (including PFS and OS) will also be done at the time of the primary analysis. However, an updated PFS analysis will also occur once the PFS censoring rate for all enrolled patients reaches 20% or after all patients have at least 1 year of follow up time (whichever occurs first). Additionally, for the purposes of OS, patients will continue to be followed until the OS censoring for all enrolled patients reaches 20% or after all patients have at least 3 years of follow up time (whichever occurs first), and the final analysis will be conducted after this milestone is reached.

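### The binary 16-week endpoint counts an event-free subject who has switched anti-cancer therapy as a regorafenib success, and does not say how withdrawn, lost or unassessed subjects are classified

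*Combined protocol and SAP*

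**What the plan says.** Section 11.2.1 makes the primary endpoint a yes/no variable recorded for every subject: "whether or not the patient experienced disease progression or death from any cause during the 16 week period following the start of treatment". Progression may be objective (section 10.2), or "progression can be subjective as determined by the Investigator" if the evidence is documented. The section has no rule for new anti-cancer therapy, withdrawal, loss to follow-up or a missing week-16 assessment, and no non-evaluable category.

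Section 11.2.2 does have such rules, but for time-to-event PFS. With new therapy before documented progression, "PFS will be censored at the date of last radiologic assessment prior to the commencement of subsequent therapy", and an event that follows a gap of two or more scheduled scans is also censored. That PFS is analysed by Kaplan-Meier as a secondary analysis (11.4.4.2).

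The surrounding text foresees the situations concerned:

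- Section 4.3.8 asks for continued imaging, on a best-effort basis, including for subjects who "discontinued study therapy due to toxicity or reasons other than progressive disease". Scans are every 8 weeks, plus or minus 2 weeks.
- Section 4.3.10 records later cancer therapies and survival status.
- Section 3.4 ends treatment and procedures for subjects who withdraw consent or are lost.
- Section 3.6: "Subjects who withdraw consent after receiving first dose of study drug will not be replaced".
- Section 11.3 analyses efficacy in all subjects who begin regorafenib.
- Section 11.4.1 runs the primary analysis once all 32 subjects have progressed, died, or "have at least 16 weeks of follow up time after the treatment start date".

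Sections 11.1 and 11.4.4.1 reject the null if at least 8 subjects are living and free of progression at 16 weeks.

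**The concern.** Two groups of subjects are affected, in different ways.

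**Switchers.** Take a subject who stops regorafenib for toxicity at week 4, starts chemotherapy at week 5 and has a stable scan at week 16. No progression or death has occurred, so the subject is a success under 11.2.1 and under the decision rule. The plan treats this subject's later PFS as uninformative about regorafenib in 11.2.2, yet counts the same outcome in regorafenib's favour in the analysis that decides the trial. Censoring cannot carry over to a yes/no variable tested by exact binomial, so the 11.2.2 protection does not reach the primary endpoint.

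**Unknown status.** Take a subject who withdraws or is lost at week 6 with no event recorded. The subject stays in the denominator and, after withdrawal of consent, is not replaced. The plan does not say whether this is a success or a failure. The subject also never meets any of the three conditions in 11.4.1, so read literally the primary analysis cannot start.

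The cut-off is 8 of 32, so one classification can reverse the conclusion. If it is left open, it will be settled after the data are seen, in a single-arm trial whose efficacy data are reviewed throughout (11.4.1).

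**Working it through.** **Inputs from section 11.1.** "A total of 32 participants will be enrolled to this study"; "A single-stage design will be used to test the hypothesis that the 16-week PFS rate is less than or equal to 0.15"; reject at 8 or more; one-sided alpha 0.10, exact binomial; alternative rate 0.35 with power of at least 90%.

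**Input not in the documents.** The number k of switched or unassessed subjects. It is assumed to be 1 to 3.

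**Step 1: reproduce the design.** With X ~ Bin(32, p):

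- P(X ≥ 8 | p = 0.15) = 0.0958, within 0.10.
- P(X ≥ 8 | p = 0.35) = 0.918, above 0.90.
- P(X ≥ 7 | p = 0.15) = 0.195, so 7 would not be an admissible cut-off.

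The design figures hold. They also show what one subject is worth: 7/32 gives p = 0.195 and the null stands; 8/32 gives p = 0.0958 and it is rejected.

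**Step 2: worst case.** All k subjects are scored as certain successes and the other 32 − k succeed at 0.15. Type I error = P(Y ≥ 8 − k), Y ~ Bin(32 − k, 0.15).

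- k = 1: P(Y ≥ 7), n = 31: 0.173
- k = 2: P(Y ≥ 6), n = 30: 0.289
- k = 3: P(Y ≥ 5), n = 29: 0.445

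This describes unassessed subjects under the reading that makes them successes.

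**Step 3: switchers.** A switcher is a success only if still event-free at week 16, so certainty is too strong. Let each succeed with probability q, assumed to be 0.25 to 0.35, and the rest at 0.15. Type I error = Σ over j = 0..k of P(J = j) × P(Y ≥ 8 − j), J ~ Bin(k, q), Y ~ Bin(32 − k, 0.15).

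For k = 1, P(Y ≥ 7) = 0.1731 and P(Y ≥ 8) = 0.0822 with n = 31:

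- q = 0.25: 0.25 × 0.1731 + 0.75 × 0.0822 = 0.105
- q = 0.35: 0.35 × 0.1731 + 0.65 × 0.0822 = 0.114

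The same sum gives 0.115–0.134 for k = 2 and 0.125–0.157 for k = 3. All exceed 0.10, because the design leaves a margin of only 0.10 − 0.0958 = 0.0042.

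**Step 4: cost of scoring these subjects as failures.** P(Y ≥ 8), Y ~ Bin(32 − k, p):

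| k | type I error (p = 0.15) | power (p = 0.35) |
|---|---|---|
| 0 | 0.096 | 0.918 |
| 1 | 0.082 | 0.899 |
| 2 | 0.070 | 0.876 |
| 3 | 0.059 | 0.849 |

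**The case against.** A reader might infer that the endpoint scores every subject without an observed event as a success, lost subjects included. The documents do not support that. Section 11.2.1 speaks of events experienced, not events observed, and the decision rule in 11.1 and 11.4.4.1 counts subjects who are living and progression free at 16 weeks, which can be read as requiring known status. The 11.4.1 trigger leaves a lost subject unresolved; it does not assign success. On unknown status the plan is silent.

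Several provisions also narrow the problem. Section 10.2 brings symptomatic deterioration into the determination of PFS, and 11.2.1 accepts documented subjective progression, so many subjects who leave because of clinical decline can already be events. Monthly contact, chart review (4.3.10) and continued imaging (4.3.8) reduce the number with unknown status. Section 2.1 says no standard second-line option exists, which may limit early switching.

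Finally, counting progression or death regardless of later therapy is a recognised approach. Under it a switcher's success is legitimate and the calculation in step 3 is not an error rate.

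These points remove the claim that missing status is scored as success, and they confine the 0.173–0.445 figures to a worst case. They do not supply a rule. Nothing requires the investigator to call progression when therapy changes, 11.2.2 shows that the plan itself does not regard later therapy as neutral, and nowhere does the plan say that it chose a treatment-regardless endpoint for the primary analysis.

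**Conclusion.** The concern holds in two parts. First, followed literally, 11.2.1 counts a subject who switches before progression and is event-free at week 16 as a regorafenib success; this is the effect of a stated rule, and it favours the drug. Second, for withdrawn, lost or unassessed subjects the plan gives no classification, and the analysis trigger is never met for those lost before week 16 without an event.

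The size depends on assumptions: 1 to 3 affected subjects, a rate of 0.15 in the others, and, for switchers, success at 0.25 to 0.35. On these, type I error is between 0.105 and 0.157 for switchers and at most 0.173 to 0.445 if every affected subject is a certain success. Both ranges lie above the stated 0.10. No dropout or switch rate in the documents allows a narrower statement. The sample size and cut-off are correct as calculated.

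**What to change.** In 11.2.1 and 11.4.4.1, define a success as a subject who is alive at week 16, has no objective or documented subjective progression, and has a progression-free disease assessment in a stated week-16 window before any non-protocol anti-cancer therapy. The window must fit the 2-week scan allowance in 4.3.8. A nominal week-16 scan may fall between weeks 14 and 18 (days 98 to 126), while the endpoint period ends at day 112, so the text should say whether a clear scan before day 112 suffices and how a scan after it counts.

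Count all other treated subjects as non-successes in the denominator of 32. Add a sensitivity analysis that counts progression or death regardless of later therapy. In 11.4.1, add withdrawal or loss to follow-up to the conditions that release the primary analysis.

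The change is a few sentences and needs no new data or procedures, since the week-16 scan and later therapies are already collected. Its cost is a slightly conservative estimate: power at 0.35 of 0.899 with one subject scored as a failure, or 0.876 with two, against 0.918. Both are below the stated 90%, the first only marginally, and 11.1 should acknowledge this.

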#### 11.2.2. Progression Free Survival

PFS is defined as the duration of time from enrollment to the study to time of

progression or death. Disease progression can be objectively determined as per Section 10.2 or progression can be subjective as determined by the investigator. Evidence for subjective progressions must be documented in the medical records. For surviving subjects who do not have documented disease progression, PFS will be censored at the date of last radiologic assessment. For subjects who receive subsequent anti-cancer therapy prior to documented disease progression, PFS will be censored at the date of last radiologic assessment prior to the commencement of subsequent therapy. Subjects who experience a PFS event immediately following an interval equal to two or more scheduled CT assessments will be censored at the date of the last assessment prior to the first missed assessment.

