### **11.3. Analysis Populations**

Efficacy and safety analyses will be conducted on the population of subjects who begin regorafenib treatment. Analysis of overall response rate will be conducted on those patients in the efficacy population with measurable disease present at baseline. The date of initiation of regorafenib treatment will be the enrollment date.

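### The missed-scan rule for Kaplan-Meier PFS turns some known deaths into censored observations, its gap can be read two ways, and nothing reconciles it with the 16-week endpoint

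*Combined protocol and SAP*

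**What the plan says.** Section 11.2.2 sets the time origin: "PFS is defined as the duration of time from enrollment to the study to time of" progression or death. Section 11.3 fixes that origin at first dose: "The date of initiation of regorafenib treatment will be the enrollment date".

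Section 11.2.2 then gives three censoring rules.

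- **Rule 1, no event:** "For surviving subjects who do not have documented disease progression, PFS will be censored at the date of last radiologic assessment".
- **Rule 2, new anti-cancer therapy before documented progression:** "PFS will be censored at the date of last radiologic assessment prior to the commencement of subsequent therapy".
- **Rule 3, missed scans:** "Subjects who experience a PFS event immediately following an interval equal to two or more scheduled CT assessments will be censored", and the censoring date is set "at the date of the last assessment prior to the first missed assessment".

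Section 4.3.8 schedules on-study scans every 8 weeks with a 2-week window either side. The baseline CT "will be performed within 28 days prior to the first dose of regorafenib (screening scan").

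The primary endpoint in Section 11.2.1 is a yes/no variable for "disease progression or death from any cause during the 16 week period following the start of treatment". It has no censoring rule. Section 11.4.4.2 uses Kaplan-Meier PFS as a secondary analysis, with landmarks at 1, 3 and 6 months. No sensitivity analysis of PFS is planned.

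**The concern.** Censoring after missed scans is normally justified because a progression first seen after a long gap cannot be dated. That reason does not apply to death, whose date needs no scan. Rule 3 makes no exception for death, and neither does rule 2.

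In this population, a subject may miss scans because of decline and then die. If so, the censoring is related to prognosis, and the Kaplan-Meier assumption of non-informative censoring is in doubt. Subjects without an on-study scan are foreseeable: Section 3.6 does not replace those who withdraw consent after dosing, Section 11.3 analyses everyone who starts drug, and Section 4.3.8 promises only best efforts for scans after treatment stops.

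Two further problems follow. Two programmers could apply rule 3 differently and obtain different curves. The same subject can also be a failure in the primary endpoint and censored in the PFS curve, with nothing in the plan to reconcile them.

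**Working it through.** **1. The plan's own figure.** Section 11.1 gives N = 32, rejection at 8 or more successes, null 0.15, alternative 0.35, one-sided alpha 0.10 and power of at least 90%. The exact binomial gives P(X ≥ 8 | 0.15) = 0.0958 and P(X ≥ 8 | 0.35) = 0.918. A cut-off of 7 gives alpha 0.195, and a cut-off of 9 gives power 0.842. The design reproduces, and no censoring rule enters it.

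**2. Where the censoring date falls.** With no on-study scan, the last scan is the screening scan, so the PFS time is between -28 and 0 days. Such a subject leaves the risk set before the first event, so every Kaplan-Meier factor 1 - d/n is the same as with censoring at day 1. A check with 4 of 32 subjects censored at week -2 or at day 1 gave identical values at weeks 8, 13, 16 and 26 (0.607, 0.357, 0.286, 0.107 for a simulated sample with true 16-week rate 0.35).

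**3. Two readings of rule 3.**

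- *Two missed scans.* With no on-study scan these are weeks 8 and 16 (window 14 to 18). A death inside 16 weeks normally cannot trigger the rule.
- *Sixteen elapsed weeks (2 × 8).* From a day -28 scan the trigger is -28 + 112 = day 84, or week 12. From day -14 it is week 14, and from day 0 it is week 16. This reading also censors a progression found at week 24 after a week-8 scan when only week 16 was missed (24 - 8 = 16 weeks).

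**4. Illustrative size at the planned landmarks (missed-scan reading).** Assumptions: exponential PFS; 3 and 6 months taken as weeks 13 and 26; a share q = 5% to 20% never scanned on study, unrelated to event time; all their events are known deaths; those after week 16 are censored at screening. Let S(t) = p^(t/16), where p is the true 16-week rate.

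- 3-month estimate: [S(13) - q·p] / [1 - q·p]
- 6-month estimate: (1 - q)·S(26) / [1 - q·p]

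| p | Landmark | All deaths counted | q = 5% | q = 20% |
|---|---|---|---|---|
| 0.35 | 3 months | 0.426 | (0.4261 - 0.0175)/0.9825 = 0.416 | (0.4261 - 0.07)/0.93 = 0.383 |
| 0.35 | 6 months | 0.182 | 0.95 × 0.1816/0.9825 = 0.176 | 0.80 × 0.1816/0.93 = 0.156 |
| 0.15 | 3 months | 0.214 | (0.2141 - 0.0075)/0.9925 = 0.208 | (0.2141 - 0.03)/0.97 = 0.190 |
| 0.15 | 6 months | 0.046 | 0.95 × 0.0458/0.9925 = 0.044 | 0.80 × 0.0458/0.97 = 0.038 |

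**5. Why the direction is not fixed.** In step 4 some removed subjects die after month 6, so both landmarks fall. Suppose instead that the k removed subjects all die between months 3 and 6. Take 32 × 0.426 ≈ 14 subjects event-free at 3 months and 32 × 0.182 ≈ 6 at 6 months, with k = 1 to 3 assumed.

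- 3 months: 14/32 = 43.8% becomes 13/31 = 41.9%, 12/30 = 40.0% or 11/29 = 37.9%.
- 6 months: 6/32 = 18.8% becomes 6/31 = 19.4%, 6/30 = 20.0% or 6/29 = 20.7%.

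A subject removed at time zero lowers each landmark before the death and raises each one after it.

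**6. Disagreement with the primary endpoint inside 16 weeks.**

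- Rule 3, elapsed-time reading from day -28: deaths in weeks 12 to 16 number 32·q·[S(12) - p], from 32 × 0.05 × (0.241 - 0.15) = 0.15 subjects to 32 × 0.20 × (0.455 - 0.35) = 0.67.
- Rule 2: if 5% to 20% are prone to start new therapy at weeks 2 to 14, with events a mean of 4 weeks later (both assumed), simulation gives 0.6 to 2.3 of 32 subjects at p = 0.15, and 0.8 to 3.3 at p = 0.35, who are failures in Section 11.2.1 but censored in Section 11.2.2.

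**The case against.** Kaplan-Meier PFS is secondary, and censoring after missed scans or new therapy is a recognised choice of estimand. Rule 3 ends by referring to the first missed assessment, which favours the missed-scan reading. Under that reading it rarely acts before week 16. Subjective progression counts as an event, so many declining subjects would have an event recorded before any long gap. These points stand, and they limit the likely size. They do not explain why an exactly dated death should be discarded, and they do not settle the wording.

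Four stronger inferences are tempting but unsupported.

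- *Every subject without an on-study scan is dated to screening.* Rule 1 covers only survivors without documented progression. Early deaths and documented subjective progressions remain events unless rule 2 or 3 applies. The 2.3-month best-supportive-care median survival in Section 11.1, taken as exponential, puts about 43% of deaths before week 8 (1 - 0.574).
- *Negative times distort the curve.* They leave it unchanged relative to day-1 censoring.
- *The rule always flatters PFS.* Steps 4 and 5 show movement in both directions.
- *Two reported 16-week PFS rates could conflict.* No 16-week Kaplan-Meier landmark is planned.

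**Conclusion.** The point holds as a defect in a secondary analysis. As written, Section 11.2.2 can discard known deaths from the planned 3- and 6-month PFS landmarks, the gap is ambiguous, and rules 2 and 3 can censor subjects whom the primary endpoint counts as failures. In the illustrations the shift ranges from under 0.01 to about 0.06, in either direction. It rests on assumed shares of unscanned subjects and assumed timing of deaths; the documents supply neither, so the true size is unknown.

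Because Section 1.1 calls PFS the primary endpoint, a reader might infer that the main result is at risk. It is not: Sections 11.2.1 and 11.4.4.1 base the test on the uncensored binary variable, and the 8-of-32 rule keeps alpha 0.0958 and power 0.918.

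**What to change.** Amend Section 11.2.2 as follows.

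- (a) Apply the missed-scan rule to progression only. Count each death without prior subsequent anti-cancer therapy as an event on the death date.
- (b) Define the gap as two consecutive missed scheduled on-study scans.
- (c) Where there is no post-baseline assessment and no event, censor at day 1. This is a clarification that leaves the curve unchanged.
- (d) Add one sensitivity analysis that counts every progression or death on its own date, regardless of missed scans or new therapy, so that it matches the primary endpoint.

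The cost is a wording change and one extra analysis of data already collected. Some PFS landmarks may become slightly less favourable. Sample size, decision rule and data collection do not change.
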